2.1.2 Secondary Objectives

To integrate the cardiovascular and ultrasound Doppler measurements into personalised computational cardiovascular models that capture changes in vascular resistances and compliances, including within retinal and uteroplacental circulations.

To collect serial urine samples for assessment of proteinuria levels (in addition to blood samples at 36 weeks for measurement of biomarkers of placental dysfunction, and data on key maternal and neonatal outcomes, collected as part of the *I-TEST* study). This will allow correlation of maternal cardiovascular changes with markers of renal microvascular dysfunction, established predictive biomarkers for placental dysfunction, and clinically relevant metrics.

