2.2 ENDPOINTS

2.2.1 Primary Endpoint

Generation of circulatory models which simulate blood flows and vascular resistances throughout the maternal circulation at serial timepoints throughout gestation.

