- Maternal ophthalmic artery Doppler measurements will be made, with waveforms obtained in sequence from the right eye, left eye, and again right and then left eye. The following four indices will be recorded: first peak systolic velocity, second peak systolic velocity, pulsatility index, and ratio of second to first peak systolic velocities (this assessment is already carried out on all *I-TEST* participants at the 36 week visit – *I-TEST-M* would involve further repeated measurements at all study visits).
- Maternal middle cerebral artery Doppler measurements will be made and the pulsatility index from both middle cerebral arteries will be recorded.
- For study visits after 25 weeks' gestation, umbilical artery and fetal middle cerebral artery
 Doppler measurements will be made and the pulsatility index of each recorded, along with the
 cerebroplacental ratio (calculated as the ratio of umbilical artery pulsatility index to fetal
 middle cerebral artery pulsatility index).

Biological samples:

[figure not shown]
 At each study visit during phase two, we will collect a urine sample for analysis of proteinuria (albumin-creatinine ratio) and for processing and storage in the Edinburgh Reproductive Tissue Biobank, allowing for future measurement of other potential biomarkers for placental or vascular dysfunction.

In addition to the serial retinal imaging carried out by I-TEST, participants recruited to phase two of I-TEST-M will undergo additional retinal imaging (scanning laser ophthalmoscopy, optical coherence tomography, and optical coherence tomography angiography) at the 6-week postnatal study visit.

[figure not shown]
Figure 1 demonstrates the schedule of visits in both phases of the study.

Figure 1: study visit schedule

Phase one: case-control study

Phase two: longitudinal cohort study (timings of study visits all +/- 3 weeks)

Additional optional fortnightly study visits. comprising cardiovascular assessment, ultrasound assessment, and repeat urine samples, for participants diagnosed with pre-eclampsia or fetal growth restriction (from diagnosis until birth)

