9.2 PROPOSED ANALYSES

Participant height and detailed cardiovascular and Doppler ultrasound data collected at study visits will be used to personalise patient-specific cardiovascular models, using a two-tier parameter estimation algorithm within a closed-loop 1D-0D circulatory model of pregnancy as described in Carson et al(13). We will extract outputs from these models including predicted measures of aortic diameter and elasticity, and retinal and placental vascular bed resistances.

We will apply correlation analysis to phase one data, to assess relationships between ophthalmic artery Doppler indices and model-predicted aortic and retinal vascular metrics. This will establish whether individual Doppler indices reflect upstream or downstream vascular properties. We will also assess correlation between ophthalmic artery and uterine artery Doppler indices which might suggest synergy between retinal and uteroplacental circulations. Descriptive statistics will be used to compare measures of ophthalmic artery blood flow and retinal vascular resistances between cases and controls, identifying possible candidate biomarkers.

In phase two, we will use a linear mixed effects regression approach to assess longitudinal changes in vascular metrics within individuals, and identify differences in metric trajectories for pregnancies affected by placental dysfunction. We will validate candidate biomarkers of vascular and placental dysfunction by testing associations with proteinuria and 36-week PIGF levels (from blood samples collected as part of the *I-TEST* study), using linear models adjusted for common co-variates, adjusting for multiple comparisons. Separate subgroup analysis will be performed for participants on antihypertensive treatment.

We will assess the relationship between estimates of retinal vascular resistances generated from computational modelling and structural parameters derived from retinal vascular imaging in the *I-TEST study*, using data from phases one and two. This will be through analysis of correlation between model-prediction retinal vascular resistance and metrics derived at the same gestation from retinal imaging, for individual participants.

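### Phase one correlates ophthalmic Doppler indices with outputs of models apparently fitted to those same indices, so it cannot settle whether an index reflects upstream or downstream vessels

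*Protocol*

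**What the plan says.** **What goes into the models.** Section 9.2: "Participant height and detailed cardiovascular and Doppler ultrasound data collected at study visits will be used to personalise patient-specific cardiovascular models". No vessel is excepted. Section 6.1 places the ophthalmic artery among the ultrasound assessments made at study visits and describes the procedure thus: "Maternal ophthalmic artery Doppler measurements will be made, with waveforms obtained in sequence from the right eye, left eye, and again right and then left". Four indices are recorded: "first peak systolic velocity, second peak systolic velocity, pulsatility index, and ratio of second to first peak systolic velocities". Section 2.1.2 gives the matching objective, "To integrate the cardiovascular and ultrasound Doppler measurements into personalised computational cardiovascular models that capture changes in vascular resistances and compliances", and names the retinal circulation among those covered.

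**What comes out.** Section 9.2 extracts predicted aortic diameter and elasticity, and resistances of the retinal and placental beds.

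**What is done with it.** In phase one, correlation analysis is applied "to assess relationships between ophthalmic artery Doppler indices and model-predicted aortic and retinal vascular metrics". The stated result is: "This will establish whether individual Doppler indices reflect upstream or downstream vascular properties".

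**How large phase one is.** Sections 4.1 and 9.1 give 10 uncomplicated and 10 disordered pregnancies. Section 9.1 offers no power calculation and calls the phase proof of principle.

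**Independent checks elsewhere.** Section 9.2 relates model-predicted retinal resistance to I-TEST retinal imaging, and phase-two candidate biomarkers to proteinuria and 36-week PlGF. It also models pregnancy outcomes. None of these is directed at the upstream or downstream origin of a Doppler index.

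**The concern.** A correlation between a measurement and a model output says something about physiology only if the output was not itself computed from that measurement. If a woman's ophthalmic waveform helps to set her fitted retinal resistance, the two will move together through the model's equations, whatever the true state of her vessels.

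The effect need not be equal on the two sides of the comparison. Section 6.1 also collects blood pressure, cardiac output, pulse wave velocity and sometimes aortic size, all of which can constrain the aortic parameters. Among the listed visit measurements, ophthalmic Doppler lies closest to the retinal bed. Reuse would therefore be expected to strengthen the retinal correlation more than the aortic one and tilt the answer towards downstream.

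What is at stake is the interpretation given to each ophthalmic index at the end of phase one. A reader would take it as a finding about the women when part of it may be a property of the fitting procedure.

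**Working it through.** The protocol gives no target correlation, alpha, power or effect size for phase one, so there is no figure of its own to reproduce. The check has three parts.

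**1. Are the indices inputs?** Section 9.2 uses the Doppler data from study visits. Section 6.1 lists ophthalmic Doppler among them. Section 2.1.2 integrates the Doppler measurements into models that include the retinal circulation. The plain reading is yes. It is not an explicit statement: section 9.2 does not itemise the signals used by the two-tier estimation and refers to a cited method paper that is not at hand.

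**2. What can reuse do?** Take a standardised index D that is unrelated to everything else in the fit, O (also standardised). Let the model output be M = w·D + (1 − w)·O. The weight w is an assumption, since the protocol gives none. Then the expected correlation is

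corr(D, M) = w / √(w² + (1 − w)²).

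For w = 0.25: 0.25 / √(0.0625 + 0.5625) = 0.25 / 0.791 = 0.32. The share of nominally significant results comes from 20,000 simulated samples of n = 20.

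| Assumed weight w | Expected r | Nominally significant at 5% |
|---|---|---|
| 0 | 0.00 | 5% |
| 0.10 | 0.11 | 7% |
| 0.25 | 0.32 | 28% |
| 0.50 | 0.71 | 96% |
| 0.75 | 0.95 | 100% |

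Unequal weights matter most here. If the index carried weight 0.50 in the retinal output and 0.10 in the aortic output, the expected correlations would be 0.71 and 0.11 with no physiological link to either. That pattern would be read as downstream. This is a linear sketch of the mechanism, not a simulation of the 1D-0D model.

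**3. What can 20 women show without any reuse?** These figures take one value per woman.

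- Fisher interval for r = 0.5: atanh(0.5) = 0.549; standard error 1/√(20 − 3) = 0.243; limits tanh(0.549 ± 1.96 × 0.243) = **0.07 to 0.77**.
- For r = 0.3 the same formula gives −0.16 to 0.66.
- The smallest |r| significant at two-sided 5% is 0.44. A true r of about 0.59 is needed for 80% power: tanh((1.96 + 0.84)/√17).
- Separating upstream from downstream means comparing two correlations that share an index. With Williams' test at n = 20, and an assumed correlation of 0.3 between the aortic and retinal outputs, simulated power is about 24% for 0.6 against 0.3, 44% for 0.7 against 0.3, and 62% for 0.7 against 0.2.

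**The case against.** **The premise is inferred.** Other vessels are scanned too, and the estimation inputs may be listed in the method paper or an analysis plan. If ophthalmic Doppler is withheld from the fit, the coupling falls away. This objection stands, so the finding is conditional. The precision problem in part 3 does not depend on it.

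**The size is unknown.** A reader might infer that the correlation is almost entirely artefact. Setting resistance equal to pressure over velocity, with assumed coefficients of variation of 15–30% for velocity and 8–10% for pressure, gives −CVv/√(CVv² + CVp²), or −0.83 to −0.97. The arithmetic is right, but the protocol does not support this as the size of the problem. It is not the closed-loop model of section 9.2, and it treats all velocity variation as unrelated to true resistance. It does not cover pulsatility index or the peak ratio, which are dimensionless, and it says nothing about the aortic outputs. At a weight of 0.10 the table above shows little harm.

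**There are other checks.** It would be wrong to say that retinal imaging is the plan's only outside check: proteinuria, PlGF and pregnancy outcomes are also used. What stands is narrower, namely that none of them tests this attribution.

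**Candidate biomarkers.** A reader might infer that these are chosen by the coupled correlation. Section 9.2 takes them from the descriptive comparison of cases with controls, and coupling alone does not create a difference between those groups.

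**The primary endpoint.** A reader might extend the criticism to "Generation of circulatory models which simulate blood flows and vascular resistances throughout the maternal circulation" in section 2.2.1, as something that merely running the fits would satisfy. That is a separate matter. A deliverable endpoint fits a primary objective of data collection, and discrimination and validation are secondary endpoints in section 2.2.2.

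**Repeated visits.** Phase one is fortnightly, so more than one value per woman may be available. Repeats from the same women are not further independent women, but the intervals above do apply only to one value each.

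**Conclusion.** The point holds in conditional form. If ophthalmic Doppler enters the fit, as sections 2.1.2, 6.1 and 9.2 read on their face, index and output are mathematically coupled. Part of the correlation is then built in, probably more on the retinal side, by an amount that the protocol does not allow anyone to compute. The range of 0.00 to 0.95 shows what reuse could do under assumed weights; it does not estimate what it will do. No planned analysis checks the attribution independently.

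Whether or not the coupling exists, the verb establish is too strong. With 20 women and one value each, r = 0.5 is compatible with anything from 0.07 to 0.77. That agrees with the proof-of-principle purpose in section 9.1 and conflicts with the conclusion claimed in section 9.2.

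This should be corrected, but it is not a fatal fault. It concerns one exploratory analysis in an observational study, and the correlations can still describe how the fitted model links index and output.

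**What to change.** 1. State in section 9.2 which Doppler signals enter the parameter estimation, and whether the ophthalmic indices are among them.
2. Answer upstream versus downstream by an in-silico sensitivity analysis: vary aortic and retinal parameters separately and read the simulated ophthalmic indices.
3. For the empirical check, correlate the indices directly with measured quantities: central pulse wave velocity, aortic size where recorded, and I-TEST retinal imaging metrics. These comparisons are valid even if pulse wave velocity or aortic size is also a model input, because no model output is involved. Use aortic model outputs only from a re-fit with ophthalmic Doppler withheld.
4. Replace the claim to establish with a statement that the analysis will explore the question, reported with 95% confidence intervals.

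The cost is extra model runs on data already planned for collection, an edit to the protocol, and a more modest stated conclusion. Aortic size is optional in section 6.1, and section 1.1 has some I-TEST women imaged only at 36 weeks, so those two comparisons may rest on fewer women or visits. No new measurement is needed.

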1.2 RATIONALE FOR STUDY

Our main aim is to identify and test novel biomarkers relating to retinal vascular, ophthalmic artery and systemic circulatory blood flows, for early detection of pregnancy complications and integration into models that are predictive of pre-eclampsia, fetal growth restriction and stillbirth. We will use a computational modelling approach to simulate blood flows within the maternal circulation and investigate the relationship between changes in the retinal and uteroplacental circulations during normal pregnancies and those affected by vascular dysfunction. This approach will complement that

of the *I-TEST* study, which aims to develop retinal imaging-derived biomarkers of placental dysfunction and within which our sub-study is nested, by relating structural retinal vascular changes with physiological adaptation of the entire maternal circulation.

We hypothesise that retinal vascular changes reflect the dynamic remodelling of maternal systemic and uteroplacental circulations during pregnancy. This could provide opportunities to monitor vascular responses to pregnancy non-invasively and in real time, allowing improved risk stratification and early detection of pregnancy complications.

To test this hypothesis and achieve our study aims, we will address the following research questions:

- 1. How do retinal blood flows change throughout gestation during uncomplicated and disordered pregnancies, and how do these changes relate to adaptation with maternal systemic and uteroplacental circulations?
- 2. Do resistance patterns within the retinal microcirculation correlate with quantitative metrics derived from retinal vascular imaging?
- 3. Do retinal blood flows correlate with established markers of placental function and clinical pregnancy outcomes?
- 4. Can integrating metrics relating to retinal vascular, ophthalmic artery or systemic circulatory blood flows into predictive models of pre-eclampsia and fetal growth restriction improve their performance, over and above current clinical tools?

We anticipate that biomarkers derived from computational models of the maternal cardiovascular system, as it evolves dynamically throughout gestation, will have utility for serial assessment of pregnant women to monitor their vascular adaptation to pregnancy. This could enable clinicians to manage pregnancies where vascular dysfunction is suspected with a more nuanced, personalised and timepoint-specific approach.

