2.2.2 Secondary Endpoints

Identification of vascular biomarkers from computational models which can discriminate pregnancies affected by placental dysfunction from healthy pregnancies.

Correlation of retinal and ophthalmic artery haemodynamic metrics derived from computational modelling with structural parameters derived from retinal vascular imaging (through comparison with *I-TEST* study results).

Validation of novel vascular biomarkers against established markers of vascular and placental dysfunction, and subsequent integration of vascular biomarkers into models which are predictive of clinical pregnancy outcomes.

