9 STATISTICS AND DATA ANALYSIS

9.1 SAMPLE SIZE CALCULATION

The emphasis of phase one is integration of measured parameters into computational models of the maternal circulation. There are no comparative pregnancy cohorts, studied using haemodynamic modelling in this way, on which to base a power calculation. Given the detailed data collected at multiple time points, and additional insights afforded by a modelling approach, a sample of 10 women with uncomplicated pregnancies and 10 with disordered pregnancies will provide proof-of-principle data and indicate potential candidate biomarkers.

Regarding phases two, there are no existing pregnancy cohorts of similar phenotypic depth studied with repeated measures. Therefore, we do not have access to estimates of effect sizes to support a formal sample size calculation. After recruitment of the first 50 women, we will use initial data to calculate effect sizes and inform data collection for further recruited participants. We propose repeated longitudinal assessment of a cohort of 100 women, and aim to recruit 115 women to allow for pregnancy losses and losses to follow up.

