In predictive outcome modelling, we will adhere to PROBAST and TRIPOD guidelines(16,17). For continuous outcomes, such as birthweight, this will be approached as a multivariate linear regression task. For categorical outcomes, including occurrence of specified pregnancy complications, we will apply a logistic regression approach only for sufficiently balanced data. Training/test data splits will be performed using k-fold cross validation. We will evaluate classifiers in terms of precision, recall and area under the receiver-operator curve, and compare these with baselines based on demographic and routine clinical evaluation data.

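### Judging added value only by cross-validated precision, recall and AUC is insensitive in about 100 women; a nested-model test should carry that conclusion

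*Protocol*

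**What the plan says.** Protocol section 1.2, research question 4, asks whether adding vascular metrics can make "predictive models of pre-eclampsia and fetal growth restriction improve their performance, over and above current clinical tools". The third secondary endpoint (2.2.2) relies on the same step, the "subsequent integration of vascular biomarkers into models which are predictive of clinical pregnancy outcomes".

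Section 9.2 sets out how categorical outcomes are handled. On the model: "we will apply a logistic regression approach only for sufficiently balanced data". Validation is by k-fold cross-validation. On the measures and the comparator: "We will evaluate classifiers in terms of precision, recall and area under the receiver-operator curve, and compare these with baselines based on demographic" factors, together with routine clinical information. No other measure is named for the classifiers, although the section commits in general to PROBAST and TRIPOD.

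On size, section 9.1 says: "We propose repeated longitudinal assessment of a cohort of 100 women". It explains that no effect sizes were available for a formal calculation. No number of affected women, significance level, classification threshold or number of folds is given.

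**The concern.** Question 4 is about added value: given the clinical predictors, does the vascular metric carry further information? The planned logistic models can answer that directly, because the baseline model is nested in the baseline-plus-metric model. Section 9.2 instead sets the terms of comparison as differences in cross-validated performance. In a cohort of this size such differences are small relative to their sampling error. Adding even a useful term also costs some cross-validated performance through estimation.

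The risk is a misleading negative answer. A metric that does add information would often show no convincing gain over the baseline, and a reader could take that as evidence that it adds nothing.

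**Working it through.** **Inputs from the protocol.** 100 women in phase two (9.1); logistic regression, k-fold cross-validation and the three named measures (9.2). There is no power figure for question 4 to reproduce.

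**Assumptions.** 20 or 30 affected women; one baseline predictor and one independent added marker, each normal with unit SD and shifted by 0.75 SD in affected women; 5-fold cross-validation; two-sided 5% level. Fewer affected women are left out because of the balance condition on logistic regression.

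**Size of the true gain.** For a normal predictor with shift d, AUC = Φ(d/√2).
- Baseline alone: Φ(0.75/√2) = Φ(0.530) = 0.70.
- Both predictors: combined shift √(0.75² + 0.75²) = 1.061, so AUC = Φ(1.061/√2) = Φ(0.75) = 0.77.
- The true gain is therefore about 0.07. Simulated mean cross-validated AUC agrees: 0.682 to 0.746 with 20 affected, 0.687 to 0.753 with 30.

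**Hand check of the nested test.** For a single added marker, approximately z = d√(n·p·(1−p)).
- 20 affected: 0.75 × √16 = 3.00; power ≈ Φ(3.00 − 1.96) = 85%.
- 30 affected: 0.75 × √21 = 3.44; power ≈ Φ(3.44 − 1.96) = 93%.
- Bonferroni for eight metrics: level 0.05/8 = 0.00625, critical z = 2.73; power ≈ Φ(0.27) = 60% and Φ(0.70) = 76%.

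This formula ignores the cost of fitting the baseline term, so it should lie slightly above the simulated values.

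**Simulated share of studies with a significant gain** (ranges are over repeated simulations)

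| Comparison | 20 affected | 30 affected |
|---|---|---|
| Nested likelihood-ratio test, one metric | 80–82% | 86–92% |
| Same, Bonferroni for 8 | 52–57% | 69% |
| Cross-validated AUC difference (DeLong), unadjusted | 15–18% | 19–21% |
| Cross-validated log or Brier score difference, unadjusted | about 5–14% across both | |

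With Bonferroni for 20 metrics the likelihood-ratio test gives 45% and 56%. Sections 6.1 and 9.2 name at least nine candidates: four ophthalmic indices, the uterine pulsatility index, aortic diameter and elasticity, and retinal and placental resistances. Adjustment for about eight is therefore realistic.

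**False positives with a useless marker.** The unadjusted likelihood-ratio test rejects in about 5–7% of studies, so its advantage is not bought with many false positives.

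**A different data model.** With logistic truth, a baseline AUC of about 0.73 and an odds ratio of 2 per SD, the true AUC gain is about 0.05. At event rates of 20%, 30% and 40%:
- unadjusted likelihood-ratio test: 70%, 78%, 82%;
- AUC difference: 8%, 12%, 15%.

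The mean cross-validated AUC gain was 0.042 with SD 0.050 at a 20% rate, a ratio of 0.84. At 30% it was 0.044 with SD 0.042, a ratio of 1.05. Both fall well short of 1.96. In this model a useless marker is declared better by the AUC test in under 1% of studies, against a nominal 2.5% in that direction, so the AUC test is conservative.

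**Sensitivity, event rates 20–30%, likelihood-ratio test against AUC difference.**
- Stronger baseline (AUC about 0.80), odds ratio 2: 65–74% against 5–8%.
- Weaker baseline (AUC about 0.63), odds ratio 2: 74–85% against 24–30%.
- Weak marker, odds ratio 1.5: 31–38% against about 2%.
- Most favourable to AUC (weak baseline, odds ratio 3, 20% events): 97% against 57%.

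**The case against.** The strongest objection is that the two approaches answer different questions. The likelihood-ratio test is in-sample and shows that a metric carries added information; cross-validated AUC estimates how well a model would perform in new women. This stands as a reason to keep the performance measures. It does not make them a sensitive basis for saying that nothing was added.

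A second objection is that the protocol says only evaluate and compare. It states no DeLong test, cut-off or rule for discarding a metric. That is correct, and the power figures for AUC depend on an assumed test. Reading point estimates instead does not rescue the comparison. With the 0.75 SD marker, cross-validated AUC rose in 90–96% of simulated studies with 20 to 30 affected, but with a useless marker it still rose in roughly 20–30%.

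Three stronger readings are tempting but are not supported:
- *The loss arises because the metrics cut or rank the predicted risk.* Log and Brier scores use the whole probability and detect less than AUC under cross-validation, so this is not the cause.
- *Recall and precision collapse, or precision is undefined, with 6 or 10 affected women.* Those results need a 0.5 cut that the protocol does not state, and event rates that its balance condition plausibly excludes. They should not be relied on.
- *Metrics will be discarded on this comparison, or calibration is ruled out.* Section 9.2 also studies biomarkers through mixed models and through adjusted linear models against proteinuria and PlGF, and models birthweight by linear regression. The commitment to PROBAST and TRIPOD means that calibration cannot be called excluded. The first secondary endpoint asks about discrimination, for which AUC is a natural measure.

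**Conclusion.** The point holds for categorical outcomes in phase two. Section 9.2 fixes measures that are insensitive to the added value that question 4 asks about, although the planned logistic models allow a much more sensitive comparison. Under the stated assumptions the contrast is about 15–21% for the AUC difference against 80–92% for the nested test. Against the adjusted figure of 52–69%, the unadjusted AUC comparison is still far behind.

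Event count, effect size, level and number of folds are all assumed. The direction was the same in every scenario examined, but the size varies. For a weak marker the nested test also misses most gains, so the size of the cohort is a limit in its own right. The study is exploratory and its other biomarker analyses are untouched. This is a worthwhile improvement to one analysis and does not undermine the plan as a whole.

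**What to change.** In 9.2, name a small set of candidate metrics before outcome data are examined. For each, fit the baseline and the baseline-plus-metric logistic models in the same women. Base the conclusion on added value on the likelihood-ratio test of these nested models, using a penalised likelihood if events are few, and extend to it the multiplicity adjustment already planned for the biomarker associations.

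Keep cross-validated AUC, precision and recall as descriptive performance measures with intervals, adding log or Brier score and calibration if wanted. State that lack of a clear gain on these measures is not a basis for concluding that a metric adds nothing.

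The cost is a few sentences and a little analysis code, with no new participants, visits or data. The downside is that the test is in-sample, so the metrics must be chosen beforehand. It also shows that information is added, not how large the clinical gain is, so it should be reported beside the performance measures.
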